Appendix B. Censoring Rules for Radiographic Progression-free Survival

Table 14-2. Censoring Rules for Radiographic Progression-free Survival

Situation up to DCO/EOS	Date of Event or Censor	Outcome
PD	Date of first detection of PD	Event
No PD, but death recorded	Date of death	Event
Subject has no post-baseline radiographic tumor assessment and a vital status of alive or unknown	First dose date of IP	Censor
Subject does not show progression according to RECIST 1.1 or bone scan using PCWG3 criteria	Date of the last scan	Censor
Subject remains on study treatment and prior scans do not show radiographic progression	Date of the last scan showing no disease progression	Censor
Subject receives subsequent therapy known or intended for prostate cancer during the study prior to the radiographic progression	Date of the last scan showing no disease progression	Censor
Subject misses >= 2 consecutive planned radiographic scans (18 weeks) or has >= 2 consecutive unreadable scans (18 weeks)	Date of the last scan showing no disease progression	Censor

Date: 24 March 2023 Page 48 of 53

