^a Results of imaging assessments conducted as standard of care may be use for screening within 30 days of start of study treatment.

^b Timing is based on first dose of Tarlatamab (cycle 1 day 1) ± 7 days for imaging assessments.

^c Per PCWG3 recommendations, the first post-treatment bone scan (at week 8) will be used as the baseline scan with which all future bone scans are compared.

^d Radiologic imaging and tumor assessments are required at screening and every 8 ± 1 weeks post-therapy initiation until clinically significant disease progression or deterioration, withdrawal of consent or start of new anticancer therapy. Every assessment must include the chest, abdomen, and pelvis, all other known sites of disease and MRI of the brain if a subject has signs or symptoms suggestive of CNS metastases. The MRI/CT can be obtained earlier if clinical deterioration necessitates an earlier scan at the discretion of the managing physician. The same contrast and modality used at screening should be used for all subsequent assessments. ^{99m}Tc-MDP bone scan is required for each radiologic imaging and tumor assessment. Tumor burden assessments will be performed based on PCWG3 guidelines (Sections 11.8 and 11.9). To confirm soft tissue disease progression, a second MRI/CT scan must be performed at least 4 weeks after the first detection of soft tissue disease progression. Confirmation of bone disease progression by bone scan should be performed per PCWG3 guidelines. Responses require confirmation by a repeat consecutive assessment at least 4 weeks after the first detection of response as measured by RECIST 1.1.

^e For subjects who discontinued treatment for any reason other than confirmed PD, every effort should be made to perform radiographic imaging (CT/MRI/bone) of the chest, abdomen, pelvis, bone, and all other known sites of disease every 3 months until documentation of confirmed PD per PCWG3 guidelines, clinical progression, start of new anticancer therapy, or up to 3 years after the first dose of tarlatamab, whichever occurs first.

2. Introduction

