Radiographic Progression:

A radiographic progression occurs if either of the following occurs:

- Progressive disease in soft tissue per RECIST 1.1.
- Bone disease progression as per PCWG3. Bone disease progression for the first post-treatment bone scan (e.g. week 8) showing two or more additional lesions relative to screening/baseline must be confirmed by the next bone

Date: 24 March 2023 Page 23 of 53

scan (e.g. week 16) showing two or more additional lesions relative to the first post-treatment bone scan (e.g. week 8). Bone disease progression for scans after the first post-treatment scan (e.g. week 16) showing two or more additional lesions relative to first post-treatment bone scan (e.g. week 8) must be confirmed by a later scan showing two or more additional lesions relative to the first post- treatment scan (e.g. week 8).

[figure not shown]
Rules to derive timepoint radiographic progression by RECIST 1.1 with PCWG3 modifications are detailed in Table 14-6.

Radiographic Progression-free Survival (rPFS)

rPFS is defined as the interval from the first dose of tarlatamab to the earlier of a radiographic progression or death from any cause. **Censoring is at the last evaluable disease assessment date (tumor assessment or bone scan) based on the** rules detailed in Appendix B.

[figure not shown]
PFS = (PD or death date - start of treatment date + 1) \times 12 / 365.25

5.4 Exploratory Endpoint-related Definitions

Date: 24 March 2023 Page 24 of 53

6. Analysis Sets

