Appendix E. Radiographic Progression per RECIST 1.1 with PCWG3 Modifications

Overall Bone Progression Status (Bone Scan)

Table 14-5. Bone Progression Status per PCWG3

Bone Progression	
Status	Definition
Non-PD	Persistence of one or more bone lesions.
PD	Bone lesions fulfilling the requirements for new lesions and confirmation of radiographic progression.
Not performed (NP)	Only relevant if a bone scan is not performed at that visit.

Radiographic Progression per RECIST 1.1 with PCWG3 Modifications

Combine RECIST 1.1 visit response collected in the data set and bone progression status (PCWG3) derived from Table 14-5 to get radiographic progression status by RECIST 1.1 with PCWG3 modifications as outlined in Table 14-6.

Table 14-6. Radiographic Progression by RECIST 1.1 with PCWG3 Modifications

RECIST 1.1 Visit Response (soft tissue/visceral)	Bone Progression Status	Bone Lesion (Present/Absent)	Timepoint Radiographic Progression by RECIST 1.1 with PCWG3 Modifications
PD	Any	Any ^b	PD
Any	PD	Any ^b	PDe
SD, Non-CR/Non-PD ^h , PR, CR	Non-PD ^f , NEB ^g , or NP ^a	Any ^b	Non-PD
NED°	Non-PD ^f	Any ^b	Non-PD
NED°	NPª	Any ^b	NEd

Date: 24 March 2023 Page 53 of 53

NEd	Non-PD ^f , or	Any ^b	NEd
	NP ^a		

- a. Bone scan was not done or issue with the quality of the image.
- b. Any result whether measured or missing.
- c. No evidence of soft tissue disease at all visits.
- d. Not evaluable.
- e. Following the confirmation of PD at the subsequent bone scan, the overall radiological visit response of progression for the visit will be programmatically derived as PD using the progression date (previous bone scan date where new lesions first seen) captured on the eCRF.
- f. See Table 14-5: Bone Progression Status per PCWG3.
- g. No evidence of bone lesion at baseline.
- h. Valid RECIST 1.1 response option only for subjects with non-measurable soft tissue disease only at baseline.

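### The SAP gives three different rPFS censoring dates for a subject without progression, and two of them can fall on a visit that its own status table rates not evaluable

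*SAP*

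**What the plan says.** Rows of Table 14-2 (SAP Appendix B) are counted here from the top.

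- **Row 3** censors at first dose, but only if the subject has no post-baseline radiographic tumor assessment and is alive or of unknown status.
- **Row 4**, "Subject does not show progression according to RECIST 1.1 or bone scan using PCWG3 criteria", censors at the last scan. It does not require that scan to be evaluable or to show absence of progression.
- **Row 5**, "Subject remains on study treatment and prior scans do not show radiographic progression", censors at "Date of the last scan showing no disease progression".
- **Row 6** (subsequent prostate cancer therapy before progression) uses the same date as row 5.
- **Row 7**, "Subject misses >= 2 consecutive planned radiographic scans (18 weeks) or has >= 2 consecutive unreadable scans (18 weeks"), also uses that date.

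The rPFS definition in SAP Section 5.3 words it a third way: "Censoring is at the last evaluable disease assessment date (tumor assessment or bone scan"), based on the Appendix B rules.

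Visit status comes from Table 14-6 in SAP Appendix E, which instructs the programmer to "Combine RECIST 1.1 visit response collected in the data set and bone progression status (PCWG3) derived from" Table 14-5. There, soft tissue NE with bone Non-PD or bone not performed gives NE. Soft tissue SD, PR or CR with bone not performed ("Bone scan was not done or issue with the quality of the image") gives Non-PD. So CT/MRI without a bone scan is enough for Non-PD, but a Non-PD bone scan beside NE soft tissue is not.

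SAP Section 5.3 applies the same censoring strategy to duration of response (DOR), whose progression event is RECIST 1.1 only.

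**The concern.** A subject on treatment without progression meets rows 4 and 5 together. The two rows word the date differently, and no order of precedence is given. Two programmers could follow the SAP and produce different rPFS curves.

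The visit that exposes the problem is a last one with a readable bone scan and a missing or unreadable CT/MRI. Protocol Section 5.1 requires measurable disease, so a bone scan alone says little about whether such a subject is progression-free. Appendix E treats the visit that way, yet row 4 and Section 5.3 both allow it to set the censoring date. The subject then stays at risk beyond the last visit at which absence of progression was established.

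Two consequences follow. A subject whose only post-baseline visit is NE is not returned to first dose, because row 3 does not apply. DOR can be extended to a bone-scan date although bone plays no part in its progression event.

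**Working it through.** **Figure to reproduce.** The SAP states no rPFS median, event count or precision, so there is none. The 18 weeks in row 7 agrees with the imaging schedule in Protocol Section 1.3 ("Radiologic imaging and tumor assessments are required at screening and every 8 ± 1 weeks post-therapy initiation"): 2 × (8 + 1) = 18.

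**The rules side by side for a censored subject whose last visit has NE soft tissue and a Non-PD bone scan**

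| Rule | Censoring date |
|---|---|
| Row 4 | this visit |
| SAP 5.3 | this visit (the bone scan is evaluable) |
| Row 5 | unclear: the bone scan shows no progression, but the visit is NE |
| Row 7 | not triggered by one such visit; for a run of them, depends on whether a readable bone scan makes the visit readable |
| Table 14-6 Non-PD as the test | the previous Non-PD visit, or first dose |

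**Direction.** The Kaplan-Meier estimate is S(t) = Π(1 − d/n) over event times, with d events among n at risk. Suppose one subject is censored earlier and an event time falls in between. The factor changes from 1 − d/n to 1 − d/(n − 1). Since d/n < d/(n − 1), the later date gives the higher curve. With no event time in between, the curves are equal. Events are not re-dated, so any bias is upward.

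**Who is affected.** Only subjects who are censored and whose last visit is NE. An NE visit followed by a Non-PD visit changes nothing, and death without progression is an event (row 2). The extra time is about one interval: 8 ± 1 weeks on treatment, or about 13 weeks with 3-monthly long-term imaging. It can be less than 8 weeks, because earlier scans are allowed and end-of-treatment or safety follow-up imaging is due when the previous scan is more than 6 weeks old. It can be more if row 7 does not catch a run of bone-only visits.

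**Size.** From the documents: 40 subjects (Protocol Section 9.2) and 8-week scans. Assumed: exponential progression with median 12, 20 or 26 weeks; 5%, 10% or 20% of visits NE, independent of progression; median dropout 52 weeks; data cutoff 26 to 104 weeks after first dose. There were 800 simulated trials per setting. Each cell is the mean excess from censoring at the last scan of any kind rather than the last Non-PD visit, with row 7 applied / not applied.

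| Median rPFS | NE rate | 26-week rate (points) | Median (weeks) | Subjects affected of 40 |
|---|---|---|---|---|
| 12 wk | 5% | 0.25 / 0.30 | 0.09 / 0.04 | 0.5 / 0.5 |
| 12 wk | 10% | 0.51 / 0.62 | 0.16 / 0.22 | 1.0 / 1.0 |
| 12 wk | 20% | 1.04 / 1.50 | 0.13 / 0.42 | 1.8 / 2.3 |
| 20 wk | 5% | 0.25 / 0.26 | 0.14 / 0.13 | 0.7 / 0.7 |
| 20 wk | 10% | 0.47 / 0.60 | 0.32 / 0.34 | 1.4 / 1.6 |
| 20 wk | 20% | 0.90 / 1.35 | 0.49 / 0.76 | 2.4 / 3.0 |
| 26 wk | 5% | 0.22 / 0.26 | 0.17 / 0.21 | 0.8 / 0.9 |
| 26 wk | 10% | 0.44 / 0.54 | 0.55 / 0.55 | 1.6 / 1.9 |
| 26 wk | 20% | 0.87 / 1.17 | 0.64 / 1.31 | 2.8 / 3.6 |

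The largest difference in a single trial was 11.6 points. The median changed in 1% to 13% of trials. The 26-week rate was never lower under the last-scan rule.

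A harsher set of assumptions has median time to end of imaging 16 or 30 weeks, 10% to 25% of last visits NE, and median rPFS 12 or 20 weeks. It gave a mean excess of 0.7 to 3.4 points at 24 weeks and 0.3 to 2.0 weeks on the median. The upper end depends on how the end of imaging is modelled, so 3.4 points is best read as an outer figure.

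**The case against.** The strongest reply is that Section 5.3 already requires the assessment to be evaluable, and row 4 should be read under that definition. This defeats one tempting inference, that the SAP instructs the analyst to censor at non-evaluable scans. It does not; the texts disagree. The reply does not settle the matter, though. Section 5.3 defers to Appendix B, where row 4 has no such condition, and a readable bone scan satisfies Section 5.3 on its own.

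It can also be said that accepting either modality is a deliberate choice, because rPFS has two components, and that no text makes Table 14-6 status the censoring test. That is fair as far as it goes. But the same SAP then declines to call the visit progression-free while letting it close the progression-free interval.

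Three limits stand:

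- Row 7 moves the date back once two or more consecutive scans are unreadable.
- The conflict with Table 14-6 needs a subject with bone lesions. The table's last row does not list the category for no bone lesion at baseline, so NE soft tissue has no stated status for those subjects.
- The protocol requires CT/MRI and a bone scan at each assessment, so bone-only visits should be uncommon.

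Moving the date back one visit also does not make the censoring non-informative if subjects leave with incomplete imaging for reasons linked to progression.

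**Conclusion.** The inconsistency is real and should be resolved before the analysis is programmed. A reader might infer that reported rPFS will be overstated. The documents support only that it can be, for censored subjects whose last visit is NE.

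The average effect is about 0.2 to 3.4 points on the 24- to 26-week rate. That range rests on NE rates and dropout patterns that the documents do not give. The simulations let every NE last visit set the date under row 4; under Section 5.3 only those with a readable bone scan would, so the effect there would be no larger. For scale, a 26-week rate of 40% (assumed) in 40 subjects without earlier censoring has a 95% half-width of 1.96 × √(0.4 × 0.6 / 40) = 0.15, or 15 points.

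rPFS is secondary and descriptive, no hypothesis is tested, and the expansion stopping rules use response and grade 4 or higher treatment-related adverse events. What is at stake is a reproducible and slightly less favourable rPFS and DOR estimate, not a trial decision.

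**What to change.** - **Rows 4 and 5 of Table 14-2, and SAP Section 5.3:** censor at the last visit with Table 14-6 status Non-PD, or at the first dose date if there is none.
- **Row 6:** the last such visit before subsequent therapy.
- **Row 7:** the last such visit before the run of missed or unreadable scans. Count a visit with soft tissue NE as unreadable, even if the bone scan is readable. Rows 6 and 7 must keep these limits, because a single unrestricted rule would drop them.
- **Table 14-6:** add the category for no bone lesion at baseline to the soft-tissue NE row, so that every visit has a status.
- **DOR:** censor at the last evaluable CT/MRI, not at a bone scan.

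The cost is SAP wording and one derivation for each endpoint. A few censoring times become shorter, so the estimates are slightly less favourable.

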8.2.2 Efficacy Assessments

8.2.2.1 Radiologic Imaging Assessment

Radiographic assessments will be obtained as scheduled in Section 1.3 irrespective of cycle duration including dose delays and treatment discontinuation.

For subjects developing COVID19 during screening period following screening imaging, consider repeating CT of chest imaging following resolution.

Standard radiological assessments should take place until clinically significant disease progression or deterioration, withdrawal of consent, or start of new anticancer therapy. Every assessment must include the chest, abdomen, and pelvis, all other known sites of disease and magnetic resonance imaging (MRI) of the brain if a subject has signs or symptoms suggestive of CNS metastases. The MRI/CT can be obtained earlier if clinical deterioration necessitates an earlier scan at the discretion of the managing physician. The same contrast and modality used at screening should be used for all subsequent assessments. ^{99m}Tc-MDP (^{99m}technetium methylene diphosphonate) bone scan is required for each radiologic imaging and tumor assessment.

Tumor burden assessments will be performed per PCWG3 guidelines (Sections 11.8 and 11.9). To confirm soft tissue disease progression, a second MRI/CT scan must be performed at least 4 weeks after the first detection of soft tissue disease progression. Responses (partial response [PR] and complete response [CR]) require confirmation by a repeat consecutive assessment at least 4 weeks after the first detection of response as measured by RECIST 1.1. Planar bone scintigraphy must be performed using

conventional ^{99m}technetium methylene diphosphonate radionuclide (^{99m}Tc-MDP) or other equivalent ^{99m}Tc-labeled radiotracers. Confirmation of bone disease progression by bone scan should be performed per PCWG3 guidelines. Disease progression based on both MRI/CT and bone scans will be used in radiographic progression endpoints (eg, radiographic PFS) evaluation. Soft-tissue progression based on MRI/CT scan will be used in response endpoints (eg, objective response and DOR) evaluation. Treatment beyond confirmed tumor progression may be allowed as per PCWG3 guidelines (Section 11.8; Scher et al, 2016). Refer to the imaging manual for details on imaging assessments.

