The subject's best response assignment will depend on the findings of both target and non-target disease and will also take into consideration the appearance of new lesions and confirmation of response. Confirmation of progressive disease is not required. Best overall response (BOR) will be based on all post-baseline disease assessments that occur prior to the initiation of subsequent anticancer treatment. At least 7 weeks from the first dose of IP must elapse without radiological disease progression to meet the minimum criteria for SD duration in order to assign a best overall response of SD. In general, subjects not classifiable under the RECIST 1.1

Date: 24 March 2023 Page 22 of 53

response categories due to inadequate data or early death will be classified as non-evaluable (NE) for BOR but will be counted in the denominator of all response rate calculations. The BOR will depend on the findings from MRI/CT scans. BOR per RECIST 1.1 has the following possible categories: complete response (CR), partial response (PR), stable disease (SD), progressive disease (PD) or not evaluable (NE). The rules for deriving the BOR are detailed in Appendix D.

Disease control rate (DCR)

DCR is defined as the **proportion** of subjects with a best overall response of confirmed response (CR/PR) or SD as per RECIST 1.1.

Duration of Response (DOR) per RECIST 1.1

DOR is defined as the time from the date of an initial objective response per RECIST 1.1 to the earlier of progressive disease per RECIST 1.1 or death for subjects with an objective response. **DOR** will be censored following the same censoring strategy as radiographic progression-free survival as detailed in Appendix B.

Objective Response (OR) per RECIST 1.1

OR is defined as best overall response of PR or CR per RECIST 1.1, confirmed by an assessment at least 4 weeks later. Subjects who do not experience a PR/CR or do not have any follow-up tumor assessments will be regarded as non-responders.

Objective Response Rate (ORR)

ORR is defined as the **proportion** of subjects with a best overall response of **confirmed** CR or PR per RECIST 1.1.

Overall Survival (OS)

OS is defined as the time from the start of treatment until event of death due to any cause. Subjects still alive will be censored at the date last known to be alive. If the date last known to be alive is after the date that triggers the analysis (i.e., the data cut-off date), the subject will be censored at the data cut-off date.

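### The 18-week missed-scan limit for censoring rPFS and DOR fits 8-weekly imaging only; on 3-monthly follow-up one missed scan already exceeds it

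*SAP*

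**What the plan says.** **Censoring rule.** SAP Appendix B, Table 14-2, has one row for assessment gaps: "Subject misses >= 2 consecutive planned radiographic scans (18 weeks) or has >= 2 consecutive unreadable scans (18 weeks". The outcome is censoring at the last scan that shows no progression. The first row of the same table makes progression an event, dated at "Date of first detection of PD", without qualification. The table gives no order of precedence between the two rows. SAP 5.3 adds that DOR "will be censored following the same censoring strategy as radiographic progression-free survival".

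**Imaging schedule.** Protocol Table 1-3 has an 8-weekly Treatment Period column and a separate long-term follow-up column that points to footnote e.

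- Footnote d requires imaging "every 8 ± 1 weeks post-therapy initiation until clinically significant disease progression or deterioration, withdrawal of consent or start of new anticancer therapy". Stopping tarlatamab is not among those end points.
- Footnote e says: "For subjects who discontinued treatment for any reason other than confirmed PD, every effort should be made to perform radiographic imaging", at 3-month intervals. Protocol 8.1.4 and the long-term follow-up definition in SAP 5.1 also set 3-monthly imaging.
- Protocol 8.2.2.1 says: "Radiographic assessments will be obtained as scheduled in Section 1.3 irrespective of cycle duration including dose delays and treatment discontinuation".
- Table 1-3 also asks for CT/MRI at the end-of-treatment or safety follow-up visit if none was done in the preceding 6 weeks.

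**The concern.** The missed-scan row states one condition in two ways, as a number of scans and as a number of weeks. The two agree only if scans are 8 weeks apart. The SAP itself provides for a phase in which they are 3 months apart and gives that phase no limit of its own. Two programmers could therefore derive different rPFS and DOR times for the same subject.

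The subjects exposed are those who left treatment without confirmed progression, responders among them. If the week limit is applied, an observed progression can become a censored time at an earlier scan. Removing events in this way raises the Kaplan-Meier curves. DOR is estimated in responders only, so a few reclassified events could move a median or a landmark.

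**Working it through.** **Inputs.** On-treatment interval 8 weeks, window ±1 week (Table 1-3, footnotes b and d). Long-term interval 3 months (footnote e, protocol 8.1.4, SAP 5.1), taken here as 12 to 13 weeks. Footnote e gives no window, so ±1 week in that phase is an assumption.

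**Formula.** With interval I, window w and k consecutive missed scans, the gap between the scans on either side is (k + 1) × I, give or take 2w.

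**Reproducing the plan's figure.** 2 × (8 + 1) = 18 weeks. This is also the longest gap that one missed 8-weekly scan can leave: 2 × 8 + 2 × 1 = 18.

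**Gaps in weeks.**

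| Schedule | None missed | One missed | Two missed |
|---|---|---|---|
| 8 weeks, ±1 | 6–10 | 14–18 | 22–26 |
| 3 months = 12 weeks, ±1 | 10–14 | 22–26 | 34–38 |
| 3 months = 13 weeks, ±1 | 11–15 | 24–28 | 37–41 |
| 3 months = 13 weeks, no window | 13 | 26 | 39 |

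On the 8-weekly schedule, 18 weeks separates one missed scan from two exactly. On the 3-monthly schedule one missed scan always passes it: the smallest value is 2 × 12 − 2 = 22.

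**The same construction for the 3-monthly phase.** 2 × (13 + 1) = 28 weeks with the window and 2 × 13 = 26 without. If 3 months is fixed at 12 weeks, the limits are 26 and 24.

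**Consequence for one subject.** Suppose the last clean scan is at week 24, the week-37 scan is missed, and progression is seen at week 50. The gap is 50 − 24 = 26 weeks, with one scan missed.

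- Scan count governs: event at week 50.
- 18 weeks governs and the progression row comes first: event at week 50.
- 18 weeks governs and the missed-scan row overrides: censored at week 24.

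**How often.** Assume each long-term scan is missed independently with probability q. For a progression found in the 3-monthly phase, the 18-week reading is triggered with probability q (the preceding scan missed) and the two-scan count with q². For q = 10% to 30% that is 10% to 30% against 1% to 9%.

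**How many subjects.** The only related figure is in protocol 2.2.2.3. In the lung-cancer study, treatment-related adverse events led to withdrawal in 3 subjects, printed as 3%; against the 70 on monotherapy it is 3/70 = 4.3%. Carried over to 40 expansion subjects, this gives 0.03 × 40 = 1.2 to 0.043 × 40 = 1.7, or about 1 to 2 subjects. Other reasons for stopping without progression would add to this, and the documents give no rate for them. Each such subject must also miss a scan and then show progression.

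**The case against.** **The condition is a count, and the weeks are a gloss.** Read that way, one missed 3-monthly scan never triggers censoring. This is a fair reading and it limits the harm, but the table does not say that the count governs. The printed 18 weeks is wrong as a gloss for the 3-monthly phase in any case.

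**Progression is an unqualified event.** The first row could be taken to settle the matter. A reader might infer instead that progressions after a gap will be discarded. The table supports neither inference, because it ranks no row above another.

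**The schedule is clear enough.** A reader might infer that the protocol puts the same off-treatment subject on two incompatible schedules. The Table 1-3 columns mostly answer this: 8-weekly on treatment, footnote e afterwards. Section 8.2.2.1 refers back to Section 1.3, which contains footnote e. What remains is that footnote d does not end 8-weekly imaging when treatment stops. The SAP mismatch does not depend on this point.

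**Fully adherent subjects.** A reader might also infer that a subject with every 3-monthly scan on time would be censored for missing two 8-weekly slots; with scans at weeks 21 and 34, the week-24 and week-32 slots are empty. That needs planned scans to mean the 8-week grid, which the long-term follow-up text does not support. The actual gap, 11 to 15 weeks, is also below 18.

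**Impact.** Nothing in the documents shows that subjects who stop for toxicity contribute the longest times, or that sites would follow different schedules. No hypothesis is tested, and the futility rule uses ORR, so no stopping decision changes.

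**Version difference.** The SAP was written to protocol amendment 6 and the protocol is at amendment 7. This does not explain the mismatch, since the SAP contains both the 3-month interval and the 18 weeks.

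**Conclusion.** The point holds as a defect in a stated threshold. The 18 weeks in Table 14-2 corresponds to two missed scans on 8-weekly imaging and to fewer than two on the SAP's own 3-monthly follow-up, where one missed scan leaves about 22 to 28 weeks. That range assumes 3 months is 12 to 13 weeks and a ±1-week window; without the window it is 24 to 26.

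The upward bias in rPFS and DOR is conditional. It arises only if the week limit governs over the count and the missed-scan row overrides the progression row. The number of subjects affected is probably small, and both endpoints are secondary and descriptive. The correction is still worth making, because it is cheap and the same row drives two endpoints.

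**What to change.** **SAP Table 14-2.**

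- Define the gap as two consecutive missed or unreadable scans on the schedule in force when they were due.
- Apply the 18 weeks to 8-weekly imaging only. Give the 3-monthly phase its own limit: about 28 weeks if a ±1-week window is adopted, about 26 if not. State how many weeks 3 months means.
- State that the row applies only when progression or death follows the gap, and how it ranks against the progression row.
- State that DOR uses the same rule.

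**Protocol.** Separately, reconcile Table 1-3 footnote d with footnote e, Section 8.1.4 and the end-of-treatment and safety follow-up scans, so that it is clear when one schedule ends and the next begins.

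**Cost.** The SAP change is wording only and needs no extra scans if 3-monthly follow-up is kept. The price is that a progression found after a longer gap counts as an event with a later, less precise date, which itself lengthens the recorded time somewhat. Settling the rule before database lock avoids choosing between readings with the data in view.
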